JTTHF	Jebsen Taylor Test of Hand Function
M1	Primary Motor Cortex
MP-RAGE	Magnetization Prepared Rapid Acquisition Gradient Echo
MACS	Manual Abilities Classification Scale
MB	Multi-band
MEP	Motor Evoked Potential
MRI	Magnetic Resonance Imaging
MT	Motor Threshold
NNL	Non-invasive Neuromodulation Laboratory
SO	Supraorbital Prominence
NIBS	Non-invasive Brain Stimulation
PP	Paired-pulse
SAE	Serious Adverse Event
SimNIBS	Simulation of Non-invasive Brain Stimulation
rTMS	Repetitive Transcranial Magnetic Stimulation
tDCS	Transcranial Direct Current Stimulation
TMS	Transcranial Magnetic Stimulation
TR	Time to Recovery
UCP	Unilateral Cerebral Palsy

1.0 Objectives

1.1 Purpose: To characterize motor cortex neurophysiology and to understand how one form of non-invasive brain stimulation (NIBS) called transcranial direct current stimulation (tDCS) changes brain excitability and behavior in children diagnosed with cerebral palsy, as compared to children with typical development (CTD).

Aim 1: Using transcranial magnetic stimulation (TMS), characterize brain excitability, specifically interhemispheric inhibition, in children with CP and CTD.

Aim 2: Evaluate the immediate effect of tDCS on brain excitability and motor performance in children with UCP and CTD.

Aim 3: Compare the responses to tDCS in each with individual estimated electric field intensity from computational modeling.

2.0 Background

2.1 Significance of Research Question/Purpose: Hemiparesis, or weakness on one side of the body, is common following stroke early in life. The broader clinical diagnosis for this type of childhood movement impairment is unilateral cerebral palsy (UCP). Cerebral palsy affects about 3 out of every 1000 live births in the United States¹, and produces lifelong motor, sensory, and cognitive disability.

Neurorehabilitation has primarily focused on intensive motor training to encourage use of the affected extremities in an effort to produce use-dependent neuroplasticity in the brain. Such interventions are effective, but require a burdensome amount of time, 60-90 hours per week, for both the child and therapist. Furthermore, some children do not respond at all to such training.

Neuromodulation is a relatively new field that aims to influence the brain's neuronal activity through direct application of magnetic (TMS) or electric (tDCS) energy. It is thought the combination of neuromodulation and motor training may reduce the dosage of training needed, and would promote recovery to a greater extent for more individuals. Indeed, previous work in adult stroke demonstrate a benefit of combining repetitive TMS (rTMS) and tDCS with motor training, compared to training alone.^{2,3} These types of synergistic interventions are just beginning to be used in children with UCP, with some preliminary data showing potential benefit.

One of the many questions surrounding neuromodulatory interventions like tDCS is how to reliably predict changes in neuronal activity. The currently hypothesized effects of tDCS are polarity-specific: anodal tDCS depolarizes membranes resulting in increased neuronal excitability; cathodal tDCS hyperpolarizes tDCS resulting in decreased neuronal excitability. Furthermore, these effects scale with the intensity of stimulation: the larger

the direct current delivered, the greater the change in excitability. This framework has been used to guide almost all studies using tDCS to produce a change in brain function and resulting behavior.

More recently, the field is beginning to appreciate that this framework may be overly simplistic. For example, when a cognitive task is performed concurrently with tDCS, there are reported non-linear effects related to current intensity and direction of change in excitability.⁴ Such work has a significant impact on the use of tDCS in rehabilitation, which advocates for the pairing of stimulation with on-going activity.

One common approach to using tDCS in individuals with stroke is to target the non-lesioned hemisphere. Following stroke, there is an imbalance of communication between brain hemispheres. This communication, known as interhemispheric inhibition (IHI), is a normal control process whereby the activated motor cortex sends an inhibitory command to the opposite motor cortex to momentarily interrupt its activity, allowing for the execution of controlled unilateral movements. IHI is exaggerated in the non-lesioned hemisphere after stroke, resulting in increased inhibition on the lesioned hemisphere.^{5,6} Applying inhibitory current to the non-lesioned hemisphere may *disinhibit* this side and allow for recovery in the lesioned hemisphere.

IHI is mediated through fibers passing through the corpus callosum and can be examined non-invasively using TMS. First and foremost, IHI has been shown to exist in children and young adults^{7,8}, indicating that this mechanism is not exclusively a feature of the developed adult nervous system. The effect of NIBS to modulated IHI has been demonstrated in adults with stroke, but less clearly in children. One reason for this is a lack of data characterizing IHI in children after perinatal brain injury. It is feasible, through ongoing adaptive and maladaptive neuroplasticity, that IHI is weakly present (or not at all) in these children as compared to adults. As studies continue to focus on NIBS interventions targeting the non-lesioned hemisphere, a more comprehensive understanding of the motor control mechanisms present in children with UCP is needed to guide these interventions. Therefore, one objective of this study is to characterize IHI of both brain hemispheres in children with UCP.

At the moment, it is unclear what the acute effects of a single session tDCS are, when paired with motor training, on brain excitability or motor performance in children with and without UCP. This leads us to designing the proposed study, which will offer insight into the mechanisms of tDCS and lead the field toward a better understanding of how tDCS be implemented in a neurorehabilitation setting for both children and potentially adults.

2.2 Preliminary Data: Data from our previous study using TMS demonstrates the potential effect of cathodal tDCS to decrease cortical excitability. In a subset of 10 children, five of who received real stimulation and five received sham stimulation, we observed a decrease in motor evoked potential (MEP) amplitude following the two-week intervention period (Figure 1). These results indicate a potential neurophysiologic effect on the non-lesioned hemisphere using a small dose (0.7 mA) of tDCS. No effects on the excitability of the lesioned hemisphere were noted.

[figure not shown]

Figure 1. Change in brain excitability following tDCS. Children receiving cathodal tDCS (red line) showed a decrease in excitability compared to those in the sham group (black line).

2.3 Existing Literature: In one study of children with UCP, Kirton et al. used repetitive TMS to down-regulate the non-lesioned hemisphere, thereby decreasing IHI, in an effort to improve function of the more-affected upper limb.⁹ They found increases in grip strength in a small sample after the real intervention compared to a sham intervention. The same group also explored IHI in CTD, showing that IHI decreased with age and was correlated with unimanual performance.

The proposed study will, at the moment, be the first to offer comprehensive data specifically on interhemispheric inhibitory control mechanisms in children with UCP. We predict that children with intact functional connections from the lesioned hemisphere will show IHI, while those with only connections from the non-lesioned hemisphere will not.

The neurophysiologic effects of tDCS have not been widely reported in children with UCP. One study showed an increase in lesioned hemisphere excitability following anodal tDCS following 10 sessions of combined motor training and tDCS.¹⁰

The proposed study is novel in that we will measure physiologic responses *immediately* following stimulation to capture the acute effect of the intervention and to potentially target its neural mechanisms. Immediate effects of tDCS are thoroughly described in healthy adult populations^{4, 11} but are less described in people with neurologic conditions. Furthermore, comparing physiologic and behavioral responses with computational modeling of electric fields produced by tDCS is a novel approach toward predicting responsiveness to brain stimulation interventions. The results from this study will help guide future usage of combined tDCS and motor training interventions in larger clinical trials.

3.0 Study Endpoints/Events/Outcomes

- 3.1 Primary Endpoint/Event/Outcome: The primary outcome is magnitude of brain excitability as measured by motor evoked potentials from TMS. The primary behavioral outcome is time to complete a novel movement task.
- 3.2 Secondary Endpoint(s)/Event(s)/Outcome(s): The secondary neurophysiological outcomes are interhemispheric inhibition as measured by ipsilateral silent period (iSP) and paired pulse (PP) TMS (see 5.2 Study Procedures). The secondary behavioral outcomes are the Box and Blocks Test and Grip Strength. Safety and tolerability of the study, as measured through our participant-report of symptoms questionnaires, are also secondary outcomes.

4.0 Study Intervention(s)/Investigational Agent(s)

- 4.1 Description: Non-invasive brain stimulation has been recently investigated for benefits in recovery of motor function in adults² and more recently in children.^{12, 13} One form, Transcranial Magnetic Stimulation (TMS), can be used in specific protocols either to test cortical excitability or as an intervention to attempt to influence cortical excitability. In this study we are using TMS only as a test to assess cortical excitability in the area of the brain known as the motor cortex or M1. Recent evidence suggests that 1.0mA and 2.0mA is well-tolerated and results in motor learning both for children with typical development¹⁴ and 1.0 mA in children with hemiparesis.¹⁵ Safety of tDCS is further demonstrated in a recent evidence based update with no reports of major adverse events following tDCS.¹⁶ Transcranial Direct Current Stimulation (tDCS) will be used as an intervention, applying stimulation continuously over a period of 20 minutes.

Testing cortical excitability: Transcranial Magnetic Stimulation (TMS): We will use a Magstim Rapid² TMS stimulator (Magstim Corp, Dyfed, UK) with a flat 70 mm figure-of-eight coil. TMS is a non-invasive method for assessing the excitability of the brain. The TMS stimulator is a non-significant risk device. The technique involves placing a special electrode on the head.

We will use a flat figure-of-eight coil with a 70-mm diameter for each loop of the figure-of-eight. The center of the coil is hand held on the scalp over the desired region to be stimulated. An electrical current is pulsed through the electrode, which creates a magnetic field. This magnetic field, in turn, creates an electric field in the surrounding area, including inside the skull, which induces an ionic current to flow on the surface of the brain. Depending on the parameters of the stimulation and the excitability of the underlying cortex, the stimulation may or may not depolarize the nerve membrane to threshold. If it does depolarize, an action potential is generated and conducted to spinal motor neurons, which, depending on their own excitability, may transmit an action potential to muscle. Ultimately, the

response is recorded MEP with electromyography (EMG) electrodes located over the target muscle.

Intervention: Transcranial Direct Current Stimulation (tDCS): One of two potential tDCS devices will be used. The first is a Soterix Medical 1x1 stimulator (Soterix Medical, New York, NY). This device is intended for the noninvasive stimulation of the cortex via transcranial current stimulation. The device is capable of direct current stimulation up to 1.5 mA and has a built-in sham condition setting. This sham stimulation feature allows for consistent application of the sham setting with ramp-up, extinguish and ramp-down modulation. As an added measure of safety, we will be using the Limited Total Energy (LTE) device which provides built-in adaptation to resistance and current. These devices are for investigational research only in the United States.

An [instructional video](#) from the Harvard Berenson- Allen Center for Noninvasive Brain Stimulation describes the use of Soterix tDCS in detail.

All investigational devices used in this study will have the following label statement: CAUTION – Investigational Device. Limited by Federal law to investigational use.

Stereotactic Neuronavigation: In order to verify our exact location over the motor cortex we will be using a computerized method of location called Stereotactic Neuronavigation (SNN-Brainsight Stereotactic Neuronavigation, Rogue Research, Montreal, Canada). Through the use of a locator situated atop the TMS device and a comparative subject- specific magnetic resonance imaging (MRI) image on a computer screen which shows the locator position, we will be able to specify the TMS hotspot location and placement of the tDCS electrodes.

Three-tesla (3T) Magnets for MRI will be used through the Center for Magnetic Resonance Research (CMRR). These devices pose a non-significant risk and have a claim of an abbreviated IDE.

- 4.2 Drug/Device Handling: All tDCS stimulators, electrodes, and related supplies will be stored in a locked closet inside the [name] laboratory space, which requires keypad access. For each study, the research team will transport the device to the testing facility (Neuromodulation Lab, [name]) for the day. The devices will be returned to the [name] lab at the end of data collection.

IND/IDE:

Device	510(k) Number(s)	Applicant
TMS	K060847, K143531	Magstim Corp US, LLC Woburn, MA

5.0 Procedures Involved

5.1 Study Design: This is a randomized, sham-controlled, double-blinded study. The intervention consists of a single, 20 minute session of tDCS paired with motor training (see Figure 2). Participants will be randomized to either real or sham tDCS. The participants and the members of the research team involved in assessments and testing will be blinded to intervention group (real or sham tDCS), but the other research staff/PI/Co-Is will be unblinded.

5.2 Study Procedures:

Pre-study

[figure not shown]

Figure 2. Pre-study timeline and study design.

Participant Screening and Enrollment

Participants will be initially screened for inclusion and exclusion criteria during a phone interview (Appendix A). Initial consent will be obtained over the phone to allow the caregiver to disclose protected health information (PHI) about his/her child. If the family is interested following this phone screen, we will obtain HIPAA consent to perform a medical record review (Appendix B and C). A review is then completed by the study medical director for review of inclusion/exclusion by history and MRI/CT radiographic reports of the brain (Appendix D). Eligibility will be verified by the principal investigator after this review. Eligibility is then discussed with the legal guardian and a formal schedule is established. A pre-study letter will then be sent (Appendix E). Informed consent/assent will be completed before on the day of the MRI acquisition.

The research team will utilize the CMRR Center's screening tools and adhere to the screening SOP during enrollment of all research participants in this protocol. The CMRR Center's screening tools and SOP are IRB approved under the CMRR Center Grant (HSC# 1406M51205) and information regarding screening procedures is publically available on the CMRR website.

Randomization

Participants will be randomly assigned to receive real or sham tDCS. Children with presence of a lesioned hemisphere MEP response may receive 1) ipsilesional anodal; 2) contralesional cathodal tDCS or 3) sham tDCS. Children without a lesioned hemisphere MEP may receive 1) contralesional anodal or 2) sham tDCS. Participants and their families will be blinded to group assignment. Participants will be unblinded after completing the study.

Magnetic Resonance Imaging (MRI) Acquisition

Location: Center for Magnetic Resonance Research (CMRR)

Time: 1 hour (including preparatory time)

MRIs will be performed at the CMRR on the University of Minnesota campus. We will obtain a structural image of brain anatomy to be used for stereotactic neuronavigation and individual brain modeling described below (Pre-Test Assessment: TMS and Computational Modeling).

Children and their caregivers will be screened using pre-approved CMRR safety screening forms. Children will change into scrubs and be given a "tour" of the scanning facility room. In our experience, this can alleviate anxiety related to MRI scanning in children. Caregivers will be allowed to watch through the control room window.

When ready, children will lie on the scanner bed comfortably with cushioning, pillows, etc. A movie of their choice will be projected behind them to watch during the scan. Scanning will consist of a localizer sequence (< 1min), and a T1-weighted magnetization prepared rapid acquisition gradient echo (MP-RAGE) sequence (spatial resolution 1 mm isotropic, < 6min), T2-weighted fast low-angle shot (FLASH) sequence (spatial resolution 0.7x0.7x4.0 mm, < 6min), a pair of diffusion scans (spatial resolution 1.5 mm³), a task fMRI blood oxygen-dependent level (BOLD) scan and a resting-state fMRI BOLD scan (spatial resolution 2mm³, TR = 0.8s, MB = 8). If image quality is not deemed acceptable, we will repeat the T1-sequence as needed. Children will be able to talk to the scan operator at any time.

Day of Study

Location: Non-invasive Neuromodulation Lab—Clinical and Translational Science Institute (CTSI) or Pediatric Brain Stimulation Lab—Center for Neurobehavioral Development (CNBD)

Time: 3 hours

Pre-Test Assessment: TMS

All procedures will be performed on the non-lesioned, then lesioned hemisphere unless noted otherwise.

- A. Motor threshold (MT): To find the motor threshold, we will begin testing at the estimated location of the hand region of motor cortex as identified on the reconstructed brain image in the stereotactic neuronavigation system. We will test at 50% MSO. The motor threshold, is defined as the lowest stimulator output that produces MEPs of at least 50 μ V on 50% (i.e. 5 of 10) trials. The location associated with the motor threshold is denoted as the motor hotspot. We will test up 100% MSO if tolerated by the participant to determine a motor threshold.
- B. MEP Amplitude: Twenty pulses will be delivered at the motor hotspot using a testing intensity equivalent to 120% of the MT.
- C. Cortical Silent Periods: Twenty pulses will be delivered at the motor hotspot using a testing intensity equivalent to 120% of the MT with the target hand muscle activated.
- D. Paired-Pulse Assessment: Using two TMS coils, a conditioning stimulus will be delivered to one hemisphere at an intensity equivalent to 100% MT. Simultaneously, a test stimulus will be delivered to the opposite hemisphere at an intensity equivalent to 120% RMT. A total of 20 pairs of stimuli will be used (10 with interstimulus interval = 10 ms, ten with interstimulus interval = 0 ms), delivered in a pseudorandom order.

Pre-Test Assessment: Behavioral

We will use the Gross Motor Function Classification Scale Score (GMFCS), and the Manual Ability Classification System (MACS) as clinical characterization of each participant. Members of the research team will assess hand function using the following measures: Assisting Hand Assessment (AHA), Box and Blocks Test, Grip Strength Dynamometry, and Jebsen Taylor Test of Hand Function (JTTHF). A novel motor performance task will also be employed to assess motor performance and potential effects of tDCS on motor learning.

Intervention

The intervention will last a total of 30 minutes, including preparatory time. Before stimulation, the area of skin underneath the electrode will be inspected for abrasions/lesions and then cleaned with an alcohol swab. We will use an M1-SO electrode montage, where one tDCS electrode is placed on the motor hotspot (M1) as determined by TMS testing, and the other electrode is placed on the supraorbital prominence (SO) of the opposite side. Sanitized rubber electrodes housed in single-use, sterile 3 cm x 5 cm sponges moistened with saline will be placed on the stimulation sites and held in place by elastic bands. To ensure adequate electrical conductance, care is taken to maintain firm contact of the sponge to the scalp. The static

impedance measurement is checked and stimulation does not proceed unless levels are within limits recommended by the tDCS device manufacturer.

Children in the sham group will receive the same procedures as the active tDCS group, yet the device will be set to an integrated sham setting which extinguishes the current after a 30 second to 1 minute ramp-up phase and gradually reintroduces the ramp-down at the end of the 20 minute session.

After the first 2 minutes of stimulation, the participant is questioned about pain at the electrode sites. If the stimulation is painful, a small amount of additional saline (2-4 mL) is added to the sponge, taking care to avoid wetting adjacent hair and thereby increasing the electrode area, and the tightness and placement of the band are checked. If pain persists, the stimulation intensity is decreased, and symptoms re-assessed. If pain still persists, stimulation is stopped and the electrode sites are checked. This procedure is repeated twice (every 5 minutes during tDCS) with saline solution (2-4 mL) added as needed.

Participants will receive a total of 20 minutes of active or sham tDCS. During stimulation, participants will practice the novel reaching task described above at a comfortable pace. No conversations between participant and researchers or caregivers will be allowed, except those that pertain to safety.

Post-intervention Assessments

Immediately following the intervention, TMS and Behavioral assessments will be performed at 0, 15, 30, and 60 minutes following the intervention (see Figure 2).

Other Procedures

Computational Modeling

Computational modeling of electric fields produced by tDCS will be performed using SimNIBS (Simulation of Non-invasive Brain Stimulation). Using T1-anatomical images, individual skull and brain anatomy will be reconstructed, and electric fields computed using a finite element method. The primary outcome is the estimated peak electric field strength for the M1-SO montage.

Safety Monitoring

We will use questionnaires (Appendix F) to document symptoms associated with non-invasive brain stimulation before and after the intervention and testing session. This tool asks participants about the presence and severity of symptoms such as tingling, itchiness, and headache. We will also measure heart rate and blood pressure before and after the procedures.

Follow-Up: A member of the research team will contact each participant and their caregivers within one week of completing the study to check for any adverse events. There is no long-term follow-up data collection planned.

- 5.3 Study Duration: Each participant will complete the study in either one day (MRI and intervention, four hours total) or on two separate days (one hour MRI, and three hours intervention). If done on two days, the MRI and intervention will be separated by no longer than a two week (14 day) period.

We expect to enroll all participants, both CTD and children with UCP, in a 24-month time period after the approval of the study.

All study procedures and data analysis will be completed within 36 months from the approval of the study.

- 5.4 Individually Identifiable Health Information: Protected Health Information will be obtained from participants in this study. A HIPAA authorization release form will be signed by the participant (if older than 18) or the parent/legal guardian of the participant (if younger than 18) to allow the researchers to use this information for research purposes.

- 5.5 Use of Radiation: N/A

- 5.6 Use of Center for Magnetic Resonance Research: This research will involve the Center for Magnetic Resonance Research (CMRR) facilities. See attached Pre-IRB approval from the CMRR.

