Important medical events are events that may not be immediately life-threatening, but are clearly of major clinical significance and may be SAEs. They may jeopardize the participant, and may require intervention to prevent one or the other serious outcomes noted above.

Individual and Entire Study Stopping Rules

- a. Death. Study stopped for both individual and entire trial. Full investigation of event explored by entire study team. The PI and Medical Director will review all details. An event report will be distributed to all governing and monitoring committees.
- b. Transient Functional Decline in Motor and/or Cognitive ability.
 - i. Entire Trial: After the first half of participants are enrolled, the PI will perform an interim safety analysis to determine if the intervention is causing harm. The primary outcome will be performance on the reaching task. We will also consider reports of any adverse events during the study or that occur after participation during a follow-up phone call with the family/participant. If the difference between sham and real tDCS groups exceeds 2 standard deviations in favor of sham tDCS, the study will be stopped at this interim for review by the PI and medical director. If they deem that the protocol has indications for change due to the differences between means, the study will be reviewed by the investigative team and will be changed and submitted for re-approval by the IRB before recommencing the study.
- c. Seizure
 - i. Individual: Removal of child from the study and from any remaining study procedures. Initiation and follow-through of safe and effective

seizure management. Refer to comprehensive seizure management outline (Appendix J) and the complete seizure observation documentation form (Appendix K). Provide Physician letter to participant. (Appendix L).

Study Medical Director Evaluation. Recommend further evaluation to the child and legal guardian for evaluation by pediatric neurologist if not the pediatrician routinely involved in the child's care.

If participant and caregiver are willing, we will assess post-seizure status and potential change of status.

An identification of causality and re-evaluation of treatment design will occur by study researchers, including consultants, medical monitor and physicians in order to proceed. All procedures will be assessed for strict adherence to all intervention steps listed in the protocol. If deviation is found, error will be corrected. Proceed with study.

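### Unblinding is not tied to the one-week adverse event call, so families may know their arm when they report delayed events

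*Combined protocol and SAP*

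**What the plan says.** The Randomization text in 5.2 of the protocol sets the blind and its end: "Participants and their families will be blinded to group assignment", and then "Participants will be unblinded after completing the study". It gives no day or event for the disclosure beyond completion.

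The Follow-Up paragraph in 5.2 says that someone on the research team "will contact each participant and their caregivers within one week of completing the study to check for any adverse events". It plans no longer-term data collection. Whether the caller is blinded is not stated. Section 5.1 blinds participants and the staff who do assessments and testing, and leaves other staff, including the principal investigator, unblinded.

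Section 5.3 shows what completion means for one participant: "Each participant will complete the study in either one day (MRI and intervention, four hours total) or on two separate days".

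Section 17.2 describes an interim safety analysis by the principal investigator once half the participants are enrolled. Of this review it says "The primary outcome will be performance on the reaching task", and it adds that the review will take account of "reports of any adverse events during the study or that occur after participation during a follow-up phone call".

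**The concern.** The call is the only contact after the session that 5.2 schedules, so it is the main planned source of information on delayed adverse events. (Section 13.1 mentions a follow-up visit to check for fatigue, but no such visit is scheduled.) Several recognised effects in 13.1, such as headache and fatigue, are subjective. Whether they are mentioned, and whether they are put down to the stimulation, depends on the child and caregiver. A family that knows the child had real current may report differently from a family that knows it was sham.

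At stake is the comparability of delayed adverse event reports between real and sham stimulation, in the final safety summary and in the interim look for harm. If the caller is also unblinded, then family, caller and interim reviewer could all know the arm.

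**Working it through.** The protocol gives no figure to reproduce. The point concerns the order of events, so the check sets the sections side by side.

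**Step 1: what completing the study means.**
- 5.3 counts completion in visit days: one day of four hours, or one hour of MRI and three hours of intervention on separate days. The call is not counted.
- The Follow-Up paragraph in 5.2 measures the call from completion, so the call falls after completion and is not part of it.
- 17.2 separates events during the study from those reported after participation by telephone.
- 11.4 ties the participant's payment to completing the study, again an individual milestone.

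For the individual participant, completion is therefore the end of the last session.

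**Step 2: the timeline.** Take the end of the intervention session as day 0.

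| Event | Earliest | Latest | Source |
|---|---|---|---|
| Symptom questionnaires | day 0, before the session | day 0, after the session | 5.2, Safety Monitoring |
| Reaching task | day 0, pre-test | day 0, 60 minutes after the intervention | 5.2 |
| Disclosure of allocation | day 0, after completion | not stated | 5.2, Randomization |
| Adverse event call | day 0 | day 7 | 5.2, Follow-Up |

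The disclosure window and the call window open at the same point and overlap. Disclosure before the call is permitted. It is not required, and no section rules it out.

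**Step 3: where the call data go.**
- 15.3 plans a mainly descriptive safety analysis giving counts and percentages of adverse events. Call reports would be included.
- 17.2 takes call reports into account at the interim review.

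**Step 4: what is not exposed.**
- 3.2 defines the secondary safety and tolerability outcome by the symptom questionnaires. These are completed around the session, while families are still blinded.
- The numeric interim threshold, a difference of more than 2 standard deviations in favour of sham, follows directly on the statement that the reaching task is the main interim measure. Read in that context it applies to the reaching task, which is measured in the session.
- The TMS and behavioural outcomes are also all measured in the session.

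**Step 5: upper limit on the number of calls.** Section 10.1 caps enrolment at 40 children with UCP and 10 typically developing children: 40 + 10 = 50 calls, and 50 / 2 = 25 at the halfway review. The Randomization text lists arms only by lesioned-hemisphere MEP status. If the typically developing children are not randomised, the figures become 40 calls and 40 / 2 = 20. These are ceilings that assume every family is told before its call. The documents do not say how many would be.

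**The case against.** The strongest objection is that the order is inferred. Disclosure and call both follow completion, and neither is placed before the other. A team could make every call first and comply fully. This stands: a reader might infer that families are in fact told before the call and that all call reports are collected unblinded, but the documents do not say so. They permit it.

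A second objection is that completion could mean the end of the whole trial. The record-keeping text in 17.1 uses the phrase that way, and on that reading every call would precede disclosure. It is the less natural reading here. The disclosure sentence is about participants, and 5.3, the Follow-Up paragraph and 11.4 all use completion for the individual. It does show that the sentence needs a defined event.

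A third objection is that little depends on the order. A reader might infer that the secondary safety outcome is biased, or that the stopping rule is. Neither follows, as Step 4 of the working shows. No formal test of delayed events between arms is planned, and at the interim the call reports are an additional consideration without a threshold. The interim reviewer is unblinded by design in any case. All of this stands, and it confines the point to delayed adverse events reported in the call.

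Finally, one might expect over-reporting after real stimulation and under-reporting after sham. That is plausible, but nothing in the documents establishes the direction.

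**Conclusion.** The point holds in a limited form. Followed as written, 5.2 lets a family learn the allocation before the adverse event call. Delayed events may then be reported with knowledge of the arm, and those reports go into the descriptive adverse event counts and the interim safety review. In a trial described as double-blinded, this is an avoidable gap.

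The conclusion rests on reading completion per participant, which the protocol's own usage supports, and on the absence of any rule that delays disclosure. At most 50 calls are open to the problem (40 if typically developing children are not randomised). How many would actually follow disclosure, and how large any bias would be and in which direction, cannot be derived from the documents. The primary outcomes, the questionnaire-based secondary safety outcome and the reaching-task threshold are untouched. This is a cheap improvement, not a threat to the main conclusions.

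**What to change.** In 5.2, Randomization, replace the disclosure sentence with one stating that allocation is revealed to the participant and family only once the one-week follow-up call has been completed and recorded. If a family cannot be reached, disclosure could wait until the one-week window has closed and the missed call has been noted.

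In 5.2, Follow-Up, state whether the caller is blinded. Where possible, give the call to one of the team members already blinded under 5.1. The two changes belong together, because a family that has been told its arm can reveal it to a blinded caller.

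The cost is a few words in 5.2 and up to about one week's extra wait before families learn the allocation. Visits, stimulation, sample size and analyses stay as they are.
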